Overview. Administration of inflammatory stimuli or cytokines to laboratory animals and humans affects reward pathways in the brain to lead to anhedonia and reduced motivation, which has been shown to be mediated by reduced synthesis and availability of striatal dopamine.²⁰⁻²⁵ We recently reported a relationship between increased inflammation (as defined by plasma CRP) and low functional connectivity between the ventral striatum (VS) and ventromedial prefrontal cortex (vmPFC), key structures that receive mesolimbic dopamine input,²⁶ in patients with MDD, in association with increased anhedonia.²⁷ Furthermore, our preliminary results also indicate that VS-vmPFC FC in MDD patients can be increased by acute administration of the dopamine precursor levodopa (L-DOPA) in association with improved motivation, but only in patients with high inflammation. Together these findings indicate that MDD patients with high inflammation have low striatal dopamine availability that drives decreased FC in reward circuitry and increased anhedonia/reduced motivation (**Figure 2A**).⁷ These data also support our hypothesis that VS-vmPFC FC in these patients can be strengthened by L-DOPA administration to lead to reduced anhedonia and improved motivation (**Figure 2B**).

This study will determine a daily dosing strategy for L-DOPA that will increase FC in VS-vmPFC reward circuitry in a 6-week randomized, double-blind, placebo-controlled, crossover study with 3 doses of L-DOPA in the R61. Data regarding the potential for L-DOPA to improve anhedonia

BH4-tetrahydrobiopterin; CRP-C-reactive protein; DDC-dopadecarboxylase; FC-functional connectivity; L-DOPA- levodopa; Phe-phenylalanine; PH-Phehydroxylase; ROS-reactive oxygen species; Tyr-tyrosine; TH-Tyrosinehydroxylase; vmPFC- ventromedial prefrontal cortex; VS-vmPFC FC.

and motivation will also be collected. Milestones for R61: To establish target engagement in the brain, we expect that at least one of 3 doses of L-DOPA will produce a mean increase in VS-vmPFC FC that is $\geq 20\%$ higher than that of placebo.

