17.0 Data Management* and Confidentiality

17.1 Statistical Analysis and Power

POWER ANALYSIS

[figure not shown]
Effect Size Estimations for Power and Go/No-Go Criteria: The relationship between VS-vmPFC FC and anhedonia from our previous dataset (n=48)²⁷ was used to estimate a clinically meaningful effect size (ES) for Go/No-Go criteria and power calculations. Mean FC scores for patients with high (≥ 5) versus low (< 5) anhedonia scores indicated a 50% difference in FC scores. Of note, a 50% difference for FC in patients with low compared to high anhedonia was stable across the low and high ends of the 95% confidence interval of the means, as determined by 1000-repetition bootstrapping of the data. Therefore, we expect that L-DOPA will produce $\geq 50\%$ increase in FC, corresponding to a mean difference of ~ 3 points on the anhedonia scale. We also anticipate a $\sim 30\%$ placebo response, consistent with the placebo response rate in MDD⁴⁵ and with the percent change in FC after acute placebo administration in our preliminary data in patients with high CRP (32%). Therefore, we expect to observe a $\geq 20\%$ separation between the L-DOPA and placebo responses, which will serve as Go/No-Go criteria for the R61. Based on a 20% difference in FC response between placebo and L-DOPA and the estimated standard deviation of this change based on

our preliminary data involving acute L-DOPA and placebo administration to high CRP patients (~1.5 x the mean difference between L-DOPA and placebo), an ES (Cohen's d_z for standardized differences) of 0.65 is anticipated.

Power Analysis for R61 Go/No-Go Criteria: Based on our estimated ES of $d_z=0.65$, 21 patients would be required for 80% and 28 patients would be required for 90% power. To account for uncertainty and bias, clinical covariates (age, sex, race and BMI) were also considered. Although none of the covariates exerted significant effects in the model, per se (all p-values >0.05), they did improve the ES for the mean difference in placebo versus L-DOPA in our preliminary data. Based on this improvement, an ES $d_z=0.97$ is estimated for the proposed separation of the means by $\geq 20\%$ when including covariates in the model. A graphical analysis of the sample size across a full range of power at the proposed ESs (with and without covariates) is provided in **Figure 1** as shown below.

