Figure 1. Estimated power for within subject comparisons of FC response to L-DOPA versus placebo in the R61 phase. Sample size (x-axis) and power values (y-axis) for ES (d_z) of 0.97 (with covariates) and 0.65 (without covariates) are provided. Relevant to the power analysis of the study based on Go/No-Go criteria for difference in response to L-DOPA versus placebo, both the treatment effect alone and the treatment effect plus covariates will exhibit power >0.8 with the proposed sample size of 30 (dashed line).

A sample size of $n=30$ will also provide sufficient power for collecting preliminary information about the relationship between change in behavior and target engagement in the brain. For example, based on the correlation between EEfRT and change in VS-vmPFC FC after acute L-DOPA in our prelim data of $r=0.6$, we will have $>95\%$ power to detect significant correlations with 30 patients.

Analytic strategy

Milestones (Go/No-Go Criteria)

Target Engagement in the Brain: VS-vmPFC FC using an objective, a priori analytic strategy, will serve as the target for physiologic response and functional improvement in the brain after administration of L-DOPA versus placebo. The relationship between VS-vmPFC FC and anhedonia from our previous dataset (n=48)²⁷ and anticipate placebo response was used to estimate a clinically meaningful effect size (ES) for Go/No-Go criteria and power calculations (see **Milestones**).

Milestone for Brain Target: At least 1 dose of L-DOPA will cause a mean increase in FC that is $\geq 20\%$ higher than placebo.

Power Analysis and Sample Size Estimation

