Sample size was estimated to have adequate power to observe statistical significance based on our preliminary data and the proposed Go/No-Go criteria described above (see **Power Analysis** section for detail). For the R61 Phase, the proposed threshold criteria for the primary outcome of target engagement in the brain (VS-vmPFC FC) is a mean change with L-DOPA from baseline of $\geq 20\%$ greater than that of placebo. Based on the means and standard deviations from our previous work, a $\geq 20\%$ difference in mean change in FC corresponds to a effect size (ES) of 0.65, indicating that with a 2-sided alpha=5%, a total of 30 patients (out of 35 that will be studied to account for potential drop-outs) will be required to have $>90\%$ power for statistical analysis (see **Figure 1** in the **Power Analysis** section of **Human Subjects** for detail). Based on our preliminary data on the relationship between change in EEfRT performance and change in VS-vmPFC FC after acute L-DOPA of $r=0.6$, we will have also have $>95\%$ power to detect correlations between change in FC and improvements in motivation, a secondary outcome to be explored.

Statistical Analysis

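### The R61 Go/No-Go rule leaves the vmPFC decision region open while calling it predefined, and the milestone sentences word a 20-percentage-point threshold as a relative increase over placebo

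*Combined protocol and SAP*

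**What the plan says.** **Region.** Section 4.0 (Study Endpoints) and the targeted-FC paragraph of Section 6.2 define the primary outcome as connectivity between a ventral striatal seed and a named vmPFC cluster (MNI 0, 44, -8; 1408 mm³). Both then allow, as an alternative, similar vmPFC regions from the group's earlier studies. Both go on to claim rigor because seeds and region are fixed in advance. Section 17.1 repeats that claim under *Target Engagement in the Brain for R61 Go/No-Go Criteria*, and under *Milestones* it describes the analytic strategy as a priori.

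**Threshold, as derived.** Section 17.1, *Effect Size Estimations*, expects at least 50% on L-DOPA and about 30% on placebo, and takes the resulting 20% "separation between the L-DOPA and placebo responses, which will serve as Go/No-Go criteria for the R61". The effect size is then set "Based on a 20% difference in FC response between placebo and L-DOPA", and a later paragraph says a 20% "difference in mean change in FC corresponds to a effect size (ES) of 0.65".

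**Threshold, as stated in the milestones.**
- Section 3.0: at least one dose "will produce a mean increase in VS-vmPFC FC that is $\geq 20\%$ higher than that of placebo".
- Section 17.1, *Milestones*: "At least 1 dose of L-DOPA will cause a mean increase in FC that is $\geq 20\%$ higher than placebo".
- Section 17.1, *Power Analysis and Sample Size Estimation*: the criterion "is a mean change with L-DOPA from baseline of $\geq 20\%$ greater than that of placebo".
- Section 17.1, *Target Engagement*: the same comparative wording again.

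None of these says what the 20% is a percentage of.

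**Side and power.** Section 4.0 lets either the left or the right striatum count toward the decision. The power paragraph is headed as being for the Go/No-Go criteria. The later *Power Analysis and Sample Size Estimation* paragraph says the sample size was chosen for statistical significance at two-sided 5%.

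**The concern.** This rule decides whether the R33 phase starts, so it should give one answer for one data set. Two features prevent that on a literal reading.

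A region cannot be both predefined and replaceable by others. If the choice were made with results in view, taking the more favorable of two regions would raise the chance of Go for an effect smaller than the one the plan calls meaningful.

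A change that is 20% greater than the placebo change is not the same quantity as a 20-point separation. At the plan's own placebo response the literal wording asks for less than a third of what the derivation asks for.

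There is also a smaller point of presentation. Go depends on the observed mean reaching a threshold, whereas the power figures describe a test against zero. A reader who sees only the power heading and the Figure 1 caption could take one for the other.

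**Working it through.** **Inputs from Section 17.1.** L-DOPA response 50%, placebo response 30%, d_z = 0.65, 30 completers, two-sided alpha 5%.

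**1. The plan's own figures.** An exact paired t-test (noncentral t) at d_z = 0.65 needs 21 patients for 80% power and 27 for 90%. The plan says 21 and 28. Power at n = 30 is 93.1%; the plan says above 90%. The stated figures are sound.

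**2. What the milestone wording can mean at a 30% placebo response.**
- Difference between responses: 50 − 30 = 20 points.
- 20% of the placebo change: 1.2 × 30 − 30 = 6 points.

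**3. Which reading the effect size supports.** The implied SD of the within-patient difference is 20/0.65 = 30.77 points.
- 20 points: d_z = 0.65, matching the plan.
- 6 points: 6/30.77 = 0.195, giving 18% power at n = 30 and needing 279 patients for 90%.

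Only 20 points fits the stated sample sizes.

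**4. Chance of Go for one comparison under the 20-point rule.** SE = 30.77/√30 = 5.618 points. P(Go) = 1 − Φ((20 − true difference)/5.618).

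| True difference | P(Go) |
|---|---|
| 0 | 0.02% |
| 10 | 3.8% |
| 20 | 50% |
| 25 | 81% |

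The smallest difference significant at two-sided 5% is about 11.5 points. A significant result between about 12 and 19 points would therefore be No-Go. This is why the 93% power is not the chance of Go.

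**5. Chance of Go for the plan's rule (any of 3 doses, either side), with and without a second region.** Multivariate normal simulation, 300,000 draws, 20-point threshold. The documents do not give the correlations or the number of alternative regions. Assumed: dose, side and region correlations of 0.5 or 0.8 in all combinations, and one alternative region with the same true effect.

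| True effect | Named cluster only | Better of two regions |
|---|---|---|
| 0 everywhere | 0.09–0.11% | 0.15–0.22% |
| 10 points everywhere | 10.6–15.6% | 15.4–26.0% |
| 0, 10, 20 points by dose (assumed pattern) | 60.4–67.1% | 70.3–82.7% |

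With a true 20 points at every dose and on both sides, the named cluster alone gives 75.0–88.6%.

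**The case against.** The strongest reply is that the documents already settle the threshold. The derivation subtracts, the power paragraph speaks of separated means, and the sentence following the relative wording equates it with a difference in mean change at an effect size of 0.65. This stands, and it limits the point to inconsistent wording.

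A reader might infer that an inert drug could pass 14% of the time on one comparison (1 − Φ(6/5.618)), or 31–44% over three doses and two sides. Those figures belong to the 6-point reading, which the plan's effect size and sample sizes exclude. A reader might also find a 26-point rule by applying 20% to the on-placebo FC level (1.2 × 130 − 130). The milestone sentences refer to an increase or a change from baseline, and 26 points would need only 17 patients for 90% power, not 28. The documents support neither.

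On the region, the alternatives are confined to the group's cited earlier work, and nothing says the choice will be made after seeing data. That is fair. The possibility is left open, not planned, and the size in step 5 is illustrative because the number of alternatives is not given. The contradiction itself needs no assumption.

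On power, the later paragraph does say it is for statistical significance. The 50% at a true 20 points is a property of any threshold on an observed mean. The power calculation is therefore not wrong.

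On side, either striatum counting, together with at least one dose, is naturally read as one side at one dose being enough. That needs no change.

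**Conclusion.** The point holds as two textual inconsistencies in the decision rule.

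- **Region.** The decision region is called predefined but is not fixed. With one alternative region assumed, a data-driven choice would lift the chance of Go at a true 10 points from 11–16% to 15–26%. It would leave an inert drug at about 0.1–0.2%, so a false Go for an inert drug is not the issue. These figures rest on d_z 0.65, 30 completers, correlations of 0.5–0.8 and an equal effect in both regions.
- **Threshold.** The milestone sentences, read literally, ask for 6 points where the derivation asks for 20. The 20-point intent can be recovered with confidence, so it would be wrong to conclude that the plan has no threshold or that its Go rule is lax.

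Secondary: the 93% power is correct for the paired test. It differs from the chance of meeting the threshold at a true 20 points, which is 50% for one comparison and about 75–89% over three doses and two sides if the effect is present everywhere.

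**What to change.** 1. In Sections 4.0 and 6.2, make the named cluster (0, 44, -8) the only Go/No-Go region. Remove the allowance for similar regions from the decision rule and report other regions as sensitivity analyses.
2. In Section 3.0 and in the three milestone statements of Section 17.1, use one sentence that matches the derivation: Go if, for at least one dose, the percent change from baseline in mean FC on L-DOPA minus that on placebo is at least 20 percentage points.
3. As a clarification, under *Power Analysis for R61 Go/No-Go Criteria* and in the Figure 1 caption, repeat that power refers to the paired significance test. Give the chance of reaching 20 points beside it, with its assumptions.

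The cost is wording only. Design, sample size and the either-side rule stay as they are. Fixing the region gives up some chance of Go for real effects compared with taking the better of two: in the assumed 0/10/20 pattern, 60–67% instead of 70–83%.

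### Section 17.1 labels the power of a single paired t-test against zero as power for the R61 Go/No-Go criteria; the chance of meeting the Go rule is not stated

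*Combined protocol and SAP*

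**What the plan says.** Section 17.1 sets the threshold first. It expects an FC increase of at least 50% on L-DOPA and about 30% on placebo, and so a 20% "separation between the L-DOPA and placebo responses, which will serve as Go/No-Go criteria for the R61". The same 20% is then the effect used for power: "Based on a 20% difference in FC response between placebo and L-DOPA and the estimated standard deviation of this change" lead to a standardized paired difference (dz) of 0.65, or 0.97 with covariates in the model.

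Under the sub-heading on power for the R61 Go/No-Go criteria, the plan states that "21 patients would be required for 80% and 28 patients would be required for 90% power". The Figure 1 legend repeats the link: "Relevant to the power analysis of the study based on Go/No-Go criteria for difference in response to L-DOPA versus placebo", it says, "both the treatment effect alone and the treatment effect plus covariates will exhibit power >0.8 with the proposed sample size of 30".

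The rule itself is in the Milestone for Brain Target: "At least 1 dose of L-DOPA will cause a mean increase in FC that is" at least 20% higher than placebo. Section 3.0 says the same: "at least one of 3 doses of L-DOPA will produce a mean increase in VS-vmPFC FC that is" at least 20% higher. Section 4.0 adds that a change in either the right or the left VS can contribute. No p-value or confidence limit is part of the rule. Sections 4.0 and 17.1 mention statistical significance only as an optional aid to choosing a dose.

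Further on in Section 17.1, under Power Analysis and Sample Size Estimation, the wording is different: "Sample size was estimated to have adequate power to observe statistical significance based on our preliminary data and the proposed Go/No-Go criteria described above". There the power at n=30 is given as above 90%, with a two-sided 5% alpha.

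**The concern.** Whether the project moves on to the R33 depends on the Go rule. A reader who sees a power figure under a Go/No-Go heading, and again in a legend that cites the Go/No-Go criteria, will naturally take it as the chance that the milestone is met. It is the chance of something else, namely rejecting a zero difference for one L-DOPA versus placebo contrast.

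The two events have different hurdles. A test against zero can succeed at an observed separation well short of 20%. The Go rule cannot, but it has several doses, and possibly two sides, through which to succeed. Because the assumed effect sits exactly on the threshold, the stated power says little about the milestone, and the plan gives no other figure for it.

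**Working it through.** **Inputs from the documents.** dz = 0.65 and 0.97, assumed difference 20%, Go threshold 20%, planned completers n = 30, two-sided alpha 5% (all Section 17.1); three doses (Section 3.0); either VS can contribute (Section 4.0).

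**Assumptions.** The 20% is in percentage points of change from baseline, L-DOPA minus placebo, as the 50% minus 30% derivation implies. Means are normal and the SD is equal across contrasts. Section 17.1 does not name the test. A paired t-test is inferred from the use of dz, the within-subject comparison, the two-sided alpha and the match below.

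**Step 1: reproduce the plan's figures.** Paired t-test against zero, noncentral t with noncentrality dz × √n:

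- dz = 0.65: 80.9% at n=21, 90.2% at n=27, 91.2% at n=28, 93.1% at n=30.
- dz = 0.97: 99.9% at n=30.

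So 21 is the smallest n for 80%. For 90%, 27 already suffices, one fewer than the stated 28. A normal approximation (19 and 25) and a one-sided test (17 and 22) fit less well.

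**Step 2: put both events on one scale.**

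- dz = 0.65: SD = 20/0.65 = 30.8 and SE = 30.77/√30 = 5.62 points. The t-test is significant once the observed separation exceeds 2.045 × 5.62 = 11.5 points. Go needs 20.
- dz = 0.97: SD = 20/0.97 = 20.6 and SE = 20.62/√30 = 3.76 points.

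**Step 3: chance of Go for one dose and side.** P(Go) = 1 − Φ((20 − true separation)/SE). At a true separation of 20 the numerator is zero, so P(Go) = 50% whatever n or dz is. At SE 5.62 it is 19% at a true 15 points, 81% at 25 and 96% at 30. In simulation at a true 20 points with dz = 0.65, 93% of trials are significant, 50% reach 20 on that contrast, and 43% are significant but fall short.

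True separation needed for a given chance of Go on one contrast:

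- dz = 0.65: 80% needs 20 + 0.8416 × 5.62 = 24.7 points; 90% needs 20 + 1.2816 × 5.62 = 27.2.
- dz = 0.97: 80% needs 20 + 0.8416 × 3.76 = 23.2 points; 90% needs 20 + 1.2816 × 3.76 = 24.8.

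**Step 4: any dose, either side.** Multivariate-normal simulation of six contrasts at n = 30 and SD 30.8, with Go if any contrast is at least 20. The correlations are assumed, since the documents give none: 0.3-0.7 between doses and 0.5-0.8 between sides. One side alone is taken as enough.

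| True separation by dose (points) | Chance of Go |
|---|---|
| No effect at any dose or side | about 0.1% |
| 0/10/20 left, 0 right | 50-51% |
| 0/10/20 both sides | 60-68% |
| 10/20/20 both sides | 73-85% |
| 20 at all six | 78-92% |
| 25 at all six | 96% or more |

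These rows are illustrations. They are not estimates of what the trial will show.

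**The case against.** The strongest defence is that the plan already words the power correctly. The Power Analysis and Sample Size Estimation text says it is for statistical significance, and the Figure 1 legend opens by naming a within-subject comparison. On that reading, the references to the Go/No-Go criteria only say where the effect size comes from. Power for significance also has a use, because Sections 4.0 and 17.1 plan comparisons of L-DOPA with placebo. This stands as mitigation: the later figure needs no change. It does not remove the label from the sub-heading and the legend, and it supplies no chance of meeting the milestone.

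A second defence is that one contrast is not the Go rule either, so 50% must not be read as the trial's chance of Go. That is correct. Several doses and sides can trigger Go, and Section 17.1 expects a separation of 20% or more, so 20 is the lower end. With 25 points throughout, the illustrative chance exceeds the stated power. Treating one side as sufficient is also an assumption: Section 4.0 says only that either side can contribute.

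A reader might go further and infer from the milestone phrases (higher or greater than placebo) that 20% is relative to the placebo change. With a 30% placebo increase the threshold would then be 1.2 × 30 = 36%, only 6 points apart. The documents do not support this. Section 17.1 obtains 20% as 50% minus 30%, calls it a separation of responses, and equates it with a difference in mean change at an effect size of 0.65. The milestone wording is looser than that derivation, and this is a matter of alignment only.

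**Conclusion.** The point holds as one of labelling and omission. The 21, 28 and above-0.8 figures are sound for one unadjusted two-sided 5% paired t-test against zero, but they are not a property of the Go rule. For a single dose and side at the assumed effect, the gap is 93% against 50% at n=30 and dz = 0.65. For the whole rule the chance is unstated. Over the illustrative cases with true effects of up to 20 points and at least one contrast at 20, it runs from about 50% to 92%, and it is higher if the true effect exceeds 20.

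Three stronger conclusions do not follow. The sample size of 30 is not shown to be too small. The t-test arithmetic is not materially wrong. The stated power is not shown to overstate the chance of Go, because the direction depends on the scenario.

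The single-contrast 50% rests only on the percentage-point reading and a symmetric sampling distribution. The other figures also need the SD implied by dz, and the any-dose figures need the assumed correlations and the assumption that one side is enough.

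**What to change.** Leave the Go rule, the sample size and the analysis as they are, and change the text as follows.

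1. In the Section 17.1 sub-heading on power for the Go/No-Go criteria and in the Figure 1 legend, describe the figures for both dz values as the power of one unadjusted two-sided 5% paired t-test of L-DOPA versus placebo against zero. This agrees with the later sample-size text. Do not call them Go/No-Go power.
2. State separately the chance of meeting the Go rule at n=30: about 50% for one dose and side at a true 20 points, with the true separations needed for 80% and 90% (24.7 and 27.2 points at dz = 0.65; 23.2 and 24.8 at dz = 0.97). Add a short any-dose table built on the sponsor's own expected effects, with a no-effect row. Show the assumed correlations as ranges and say whether one side alone is enough. Section 5.0 describes the preliminary data as a single acute dose, so they cannot supply a correlation between doses.
3. As a minor alignment, word the milestone in Section 3.0 and Section 17.1 as percentage points, L-DOPA minus placebo.

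The cost is wording and one small table, with no extra patients. The downside is that the stated chance of success may look less favourable, and the table rests on correlations that must be assumed.
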